6.3 Procedure/Colonoscopy Visit (Visit 3)

If the subject is participating in the PK subset, additional laboratory samples will be obtained for sodium picosulfate and BHPM at the following timepoints:

- 15 minutes before the second dose of IMP
- 1 to 2 hours after the second dose of IMP
- 3 to 6 hours after the second dose of IMP

Immediately prior to the colonoscopy, a PK sample will be obtained for **all participating subjects** in the study (approximately 2 hours prior to the colonoscopy).

Before the colonoscopy, the following will be performed:

- Treatment completed
- Collect Subject Diary Card
- Collect the Acceptability and tolerability completed questionnaire*
- Obtain orthostatic vital signs (blood pressure and pulse)
- Measure body weight
- Obtain laboratory sample (chemistry, hematology)
- Adverse events (recorded by study personnel)
- Document any concomitant medications

- PK subset only: PK samples for sodium picosulfate and BHPM 15 minutes before the second dose, and 1 to 2 hours and 3 to 6 hours after the second dose of the IMP
- All subjects: PK sample immediately prior to colonoscopy (approximately 2 hours prior to the colonoscopy)
- Perform study drug accountability by the unblinded coordinator or unblinded pharmacist (if applicable)

*Subjects should be instructed to fill out the questionnaire during the visit in a private area prior to contact with the Investigator and to return the completed questionnaire to the study coordinator. If the coordinator is not available during the procedure, the subject will put the completed questionnaire in a sealed envelope and provide it to a member of the surgical team. The study coordinator should check each questionnaire for completion, and if the subject did not answer all/some of the questions, note the reasons on the first page of the questionnaire. No one (including study coordinator or a family member) should interpret questions or response choices for the subject.

During the colonoscopy procedure, the blinded endoscopist will:

- Video-record the colonoscopy
- Use the Modified Aronchick Scale (see [Appendix C](#)) to score the quality of the bowel preparation in the overall colon after use of the study drug
- Use the Boston Bowel Preparation Scale (see [Appendix C](#)) to score the quality of the preparation in the different segments of the colon after use of the study drug
- Record the outcome of the colonoscopy

After the colonoscopy procedure, the following will be performed/recorded:

- Adverse events (additional to those recorded prior to colonoscopy)
- Measure orthostatic vital signs (blood pressure and pulse)
- ECG
- Urinalysis (including urine osmolality, which will be collected at this visit only)
- Directed physical Examination

The subject will be scheduled to return in 1-2 days for a Follow-Up Visit (V4, see Section [6.4](#)).

6.4 Follow-up Visit (Visit 4)

Follow-up visit (Visit 4) takes place 1 – 2 Days after the colonoscopy. The Investigator will perform the following:

- A directed physical examination
- Measure orthostatic vital signs (blood pressure and pulse)
- Measure body weight
- Interview the subject about any changes in concomitant medications, concomitant illness, or any new illnesses since the last visit. New illnesses or worsening in concomitant illnesses should be reported as AEs
- Obtain central laboratory sample: chemistry and hematology
- Urinalysis
- ECG

The subject will be scheduled to return in seven (7) days (± 2 days) for a Follow-Up Visit (V5, see Section 6.5).

6.5 Follow-up Visit (Visit 5)

Follow-up visit (Visit 5) takes place seven (7) days (± 2 days) after the colonoscopy. The Investigator will:

- Perform a directed physical examination
- Measure orthostatic vital signs (blood pressure and pulse)
- Measure body weight
- Interview the subject about any changes in concomitant medications, concomitant illness, or any new illnesses since the last visit. New illnesses or worsening in concomitant illnesses should be reported as AEs
- Obtain central laboratory sample: chemistry and hematology
- Urinalysis
- ECG

The subject will be scheduled to return in twenty-eight (28)-Days (± 2 Days) for a Follow-Up Visit (V6, see Section 6.6).

6.6 Follow-up Visit (Visit 6)

Follow-up visit (Visit 6) takes place twenty-eight (28) Days (\pm 2 Days) after the colonoscopy. The Investigator will:

- Perform a directed physical examination
- Measure orthostatic vital signs (blood pressure and pulse)
- Measure body weight
- Interview the subject about any changes in concomitant medications, concomitant illness, or any new illnesses since the last visit. New illnesses or worsening in concomitant illnesses should be reported as AEs
- Obtain central laboratory sample: chemistry and hematology
- Urinalysis
- ECG

6.7 Trial Assessments

Table 1 Trial Assessment Table

Visit	1 Screening	2 Randomization	3 Procedure	4 Follow-up	5 Follow-up	6 Follow-up (EOT)
Timing versus Procedure	≤21 Days	≤10 Days	Colonoscopy (T = 0)	1-2 Days	7 Days (± 2 Days)	4 Weeks (± 2 Days)
Informed consent	x					
Inclusion/exclusion criteria	x	x				
Demographic & Medical History	x					
Body weight, Height ¹	x	x	x	x	x	x
Urine/Serum Pregnancy Test	x	x ⁷				
Schedule colonoscopy	x					
Laboratory (chemistry, coagulation, hematology)	x ²		x	x	x	x
PK sampling			x ^{3,4}			
Urinalysis	x		x ⁵	x	x	x
ECG	x		x	x	x	x
Physical examination	x		x	x	x	x
Orthostatic vital signs (BP, pulse)	x	x	x	x	x	x
Concomitant medications	x	x	x	x	x	x
Adverse events	x	x	x	x	x	x
Dispense fluid intake diary and study medication		x				
Subject Tolerability Questionnaire			x			
Perform and video-record colonoscopy			x			
Score overall colon preparation – Modified Aronchick scale			x			
Score colon segments preparation – Boston Bowel Preparation Scale			x			
Drug accountability ⁶			x			

 Height will only be collected at screening. Coagulation samples will only be collected at screening. In a subset of subjects, PK samples for sodium picosulfate and BHPM will be taken 15 minutes before the second dose, and 1 to 2 hours and 3 to 6 hours after the second dose of the Sodium Picosulfate, Magnesium Oxide and Anhydrous Citric Acid. All subjects will have a PK sample drawn immediately prior to colonoscopy (approximately 2 hours prior to the colonoscopy). At the colonoscopy visit, the urinalysis panel will include urine osmolality. Drug accountability will be performed by an unblinded coordinator or unblinded pharmacist (if applicable) and an unblinded monitor only. Premenopausal women of childbearing potential must have a urine pregnancy test performed within 3 days prior to colonoscopy. For 						

women of childbearing potential **randomization must occur within 3 days prior to colonoscopy**

7 TRIAL ASSESSMENTS

The efficacy of the colon cleansing will be measured by a blinded endoscopist using the Modified Aronchick Scale and The Boston Bowel Preparation Scale. The endoscopist performing the colonoscopy and evaluation will be blinded to the treatment.

7.1 Assessments Related to Endpoints

7.1.1 The Modified Aronchick Scale

The efficacy of overall colon cleansing will be measured by a blinded endoscopist using the Modified Aronchick scale. The overall colon will be graded as “Excellent”, “Good”, “Fair”, or “Inadequate” according to the definitions in [Table 2](#).

Table 2 Modified Aronchick Scale

Grade	Description
Excellent	>90% of mucosa seen, mostly liquid stool, minimal suctioning needed for adequate visualization
Good	>90% of mucosa seen, mostly liquid stool, significant suctioning needed for adequate visualization
Fair	>90% of mucosa seen, mixture of liquid and semisolid stool, could be suctioned and/or washed
Inadequate	<90% of mucosa seen, mixture of semisolid and solid stool which could not be suctioned or washed

The subject is considered to be a responder if overall colon cleansing equals “excellent” or “good” on this four-point scale.

The blinded endoscopist will record in the eCRF whether or not the colonoscopy was completed. If the colonoscopy was not completed, he/she will need to state the reason why and whether a repeat is required.

7.1.2 The Boston Bowel Preparation Scale

The efficacy of right colon cleansing, transverse colon cleansing, and left colon cleansing will be measured by a blinded endoscopist using the Boston Bowel Preparation Scale after washing/suctioning. Colon cleansing will be graded 0, 1, 2, or 3, according to the definitions in The Boston Bowel Preparation Scale (see [Appendix C](#)).²

[figure not shown]

Figure 2 The Boston Bowel Preparation Scale

- 0 Unprepared colon segment with mucosa not seen due to solid stool that cannot be cleared.
- 1 Portion of mucosa of the colon segment seen, but other areas of the colon segment not well seen due to staining, residual stool, and/or opaque liquid.
- 2 Minor amount of residual staining, small fragments of stool and/or opaque liquid, but mucosa of colon segment seen well.
- 3 Entire mucosa of colon segment seen well with no residual staining, small fragments of stool or opaque liquid.

Each region of the colon receives a “segment score” from 0 to 3, and these segment scores are summed for a total BBPS score ranging from 0 to 9. The maximum BBPS score for a perfectly clean colon without any residual liquid is 9, and the minimum BBPS score for an unprepared colon is 0. If an endoscopist aborts a procedure due to an inadequate preparation, then any non-visualized proximal segments are assigned a score of 0.

Both the Modified Aronchick scale and BBPS Scale are attached as [Appendix C](#).

7.1.3 Mayo Clinic Bowel Preparation Tolerability Questionnaire

A secondary efficacy endpoint will be assessed by the validated³ Mayo Clinic Bowel Preparation Tolerability Questionnaire. This questionnaire will be administered to the subject at Visit 3 on the day of the colonoscopy procedure. The Mayo Clinic Bowel Prep Tolerability Questionnaire is a simple, comprehensive questionnaire developed to evaluate the tolerability of various types of bowel preparations. The Mayo Clinic Bowel Preparation Tolerability Questionnaire is attached as [Appendix D](#).³

7.2 Other Assessments

7.2.1 Physical Examinations

A complete physical examination will be conducted at the investigational site at Visit 1. At the other scheduled visits (and at early termination if applicable), a directed physical examination will be performed. Height will be measured at Visit 1 only, but weight will be measured in every visit.

After study drug administration, any new abnormal findings or worsening of an ongoing abnormal condition will be recorded as an AE.

7.2.2 Orthostatic Vital Signs

Orthostatic vital signs (blood pressure and pulse) will be measured at each scheduled visit (and at early termination, if applicable) as follows. Blood pressure and pulse will be measured after at least 5 minutes of rest in supine position and after 3 minutes in standing position. Standing measurements should be repeated after 10 minutes in patients with symptoms of volume depletion (e.g. mild dizziness) that have not presented changes in orthostatic vital signs after 3 minutes of standing.

7.2.3 Clinical Laboratory Variables

All laboratory measurements will be performed using appropriately validated methods by a central laboratory selected by the Sponsor. Sample handling and storage will be provided to all sites directly from the central laboratory.

Laboratory values will be reported to the Investigator and Sponsor (or the Sponsor's representative) and will automatically be uploaded to a database. The database will be maintained by a clinical research organization selected by the Sponsor.

Out of range values will be described in the laboratory manual to be provided by the central laboratory. Investigators will assess all out of range values as being either clinically significant or not clinically significant via the eCRF. Clinically significant abnormal laboratory measurements should be reported as AE.

Sites will be specially instructed to review all laboratory results in order to determine if the subject is eligible for study participation and to determine any adverse events post study drug administration.

Sites will be provided with sampling supplies and materials for shipment and a manual detailing all sample collection and shipment procedures.

Following Screening Visit (V1, see Section 6.1), subjects with clinically significant abnormal laboratory values will not be randomized into this study.

The following values will be collected and sent out to the central laboratory at all study visits except the randomization visit.

- Hematology panel:
 - Full CBC and differential
- Full chemistry panel:
 - Serum Chemistry: serum osmolality, bicarbonate, fasting glucose, blood urea nitrogen (BUN), creatinine, magnesium, potassium, sodium, chloride, calcium, protein total, albumin, bilirubin total, alkaline phosphatase, aspartate aminotransferase (AST), alanine aminotransferase (ALT), and gamma glutamyl transferase (GGT)
 - Calculated creatinine clearance and BUN/creatinine ratio
- Urinalysis panel (at the colonoscopy visit (V3), this includes urine osmolality)

The following values will be collected at the site during the Screening Visit only (see Section 6.1):

- Serum pregnancy test for premenopausal female subjects
- Coagulation Panel:
 - PT, APTT

The following value will be collected during Randomization Visit only (V2, see Section 6.2):

- Urine pregnancy test (onsite) for premenopausal female subjects

The Investigator will review the laboratory results and evaluate and document whether the results are normal or abnormal and whether abnormal results are non-clinically or clinically significant. The Laboratory Report will be signed and dated by the Investigator.

7.2.4 ECG

A standard 12-lead ECG will be performed as indicated in [Table 1](#) Trial Assessment Table. After at least a 5-minute rest in a supine position, an ECG will be obtained at each visit (and at early termination, if applicable). Additional ECGs may be obtained if clinically indicated.

At each visit when an ECG is done, the investigator must review and initial the tracing. The tracing must then be stored with the subject's source documents.

The baseline ECG performed at the Screening Visit must be reviewed for major abnormalities before dosing.

If the ECG findings are clinically relevant and would prevent the subject from participating in the study (taking into account the subject's overall status), the subject should not receive the IMP.

All other abnormalities noted on the baseline ECG are reported in the Medical History eCRF. Clinically relevant abnormalities noted after the baseline ECG (Randomization Visit) should be recorded as AE

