8 ADVERSE EVENTS

8.1 Adverse Event Definition

An adverse event is any untoward medical occurrence in a subject participating in a clinical trial. It includes:

- Any unfavourable and unintended sign, symptom, or disease, whether or not considered to be caused by the IMP
- Adverse events commonly observed and adverse events anticipated based on the pharmacological effect of the IMP
- Any laboratory abnormality, vital sign, or finding from physical examination assessed as clinically significant by the Investigator. [Note: pre-existing conditions diagnosed through assessments and examinations at the Screening Visit (V1, see Section 6.1) or during the screening period are not adverse events, but are recorded as medical history]
- Accidental injuries, reasons for any change in medication (drug and/or dose), reasons for any medical, nursing, or pharmacy consultation, or reasons for admission to hospital or surgical procedures
- Overdoses and medication errors with and without clinical consequences

An adverse drug reaction (ADR) is an AE evaluated by the investigator as having a reasonable possibility of being related to treatment with the IMP.

A serious ADR is a serious adverse event (SAE) evaluated by the investigator and/or by Ferring as having a reasonable possibility of being related to treatment with the IMP.

An unexpected AE is an AE not identified in nature, severity, or frequency in the section “Undesirable Effects” in the sponsor’s current Investigator’s Brochure and current approved label.

A treatment-emergent AE is any AE that begins during the treatment period, or is a worsening of a pre-existing medical condition. The treatment period is defined as the period during which a subject receives IMP.

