9.8.4.2 ECGs

The incidence of clinically significant changes in ECGs will be summarized separately by treatment group and scheduled time point.

ECGs at each evaluation will be listed for the safety dataset. Subjects with abnormal values will be noted on the data listings.

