#### **10.4.2 ECGs**

Overall ECG assessment will be categorized as 'normal', 'abnormal, not clinically significant', or 'abnormal, clinically significant' (as judged by the Investigator). These categorized values will be summarized by treatment for each assessment time for the safety population.

QTc will be calculated both using Bazett's and Fridericia's correction formulae (see below for definitions).

---

1) Bazett's correction (square root):

$$QTcB = QT / (RR)^{0.5}$$

2) Fridericia's correction (cube root):

$$QTcF = QT / (RR)^{1/3}$$

where RR is in sec (=1 for HR=60 bpm), whereas QT is in msec.

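### SAP 10.4.2 tabulates ECG status by visit, so the incidence of clinically significant ECG changes named in the protocol is never produced; Protocol 7.2.4 also needs a new-or-worse condition and one consistent baseline visit

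*Protocol*

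**What the plan says.** **Endpoint and planned table.** Protocol 2.2 and SAP 2.2 list clinically significant changes in ECGs within a secondary safety endpoint. Protocol 9.8.4.2 states the output: "The incidence of clinically significant changes in ECGs will be summarized separately by treatment group and scheduled time point".

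**What the SAP tabulates.** SAP 10.4.2 puts each overall ECG assessment into one of three investigator ratings: normal, abnormal but not clinically significant, or abnormal and clinically significant (abnormal-CS below). It continues: "These categorized values will be summarized by treatment for each assessment time for the safety population". SAP 10.4.2.1 adds descriptive statistics for PR, QRS and QTc, both observed and as change from baseline. The criteria in Appendix 1, Table 4, which depend on a normal baseline or on a change from it, are used in SAP 10.4.2.2 for listings.

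**Baseline.** SAP 10.3 (laboratory) and 10.4.1 (vital signs) define baseline as the last assessment before the first dose of study drug. SAP 10.4.2 has no such sentence for ECG.

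**Adverse event rule.** Protocol 7.2.4 first places the baseline at screening: "The baseline ECG performed at the Screening Visit must be reviewed for major abnormalities before dosing". Findings that do not keep the subject out are handled as follows: "All other abnormalities noted on the baseline ECG are reported in the Medical History eCRF". Its last sentence reads: "Clinically relevant abnormalities noted after the baseline ECG (Randomization Visit) should be recorded as AE".

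**The concern.** A status table answers a different question from the one in the endpoint. It shows how many subjects have a clinically significant abnormality at a visit, not how many acquired one. Protocol 7.2.4 keeps a subject from dosing only if the finding is clinically relevant and would also prevent participation, so some dosed subjects may already be abnormal-CS at screening. Each of them who keeps that rating is counted again at Visits 3, 4, 5 and 6. If the SAP is followed as written, a protocol-specified safety output is missing and no one has said so.

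The AE sentence in Protocol 7.2.4 is a related but smaller matter. It does not ask that the abnormality be new or worse, and it attaches the baseline to a visit with no scheduled ECG. Two sites could record the same unchanged ECG differently.

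**Working it through.** The plan gives no figure for ECG abnormalities, so there is nothing to reproduce. The check compares the texts and then uses assumed rates to show scale.

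**1. Is the promised output anywhere in the SAP?**

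| SAP item | What it gives | Incidence of clinically significant change? |
|---|---|---|
| 10.4.2 overall rating | Counts per category at each time, by arm | No; not cross-classified by baseline |
| 10.4.2.1 PR, QRS, QTc | Summary statistics, including change from baseline | No; describes the distribution of intervals, not the number of subjects with a significant change |
| Appendix 1 Table 4, through 10.4.2.2 | Listing of subjects | No; not tabulated |
| Section 12 | Declares removal of the markedly abnormal vital signs table | ECG omission not declared |

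**2. Can it be recovered from the status table?** Let C0 be the number abnormal-CS at baseline, Cv the number at a visit, and N the arm size, with complete data. Between 0 and min(C0, Cv) of the baseline cases may persist when N is large. The number newly abnormal-CS therefore lies between max(0, Cv − C0) and Cv. Take N = 450 and an assumed 2% at baseline, so C0 = 450 × 0.02 = 9. If the visit shows Cv = 13, the new cases lie between 13 − 9 = 4 and 13. The column totals do not determine the endpoint.

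**3. How far can the level be inflated?** Assume a share q is abnormal-CS at screening and stays so, and that 1% of the others become abnormal-CS. The status count per arm is 450 × [q + (1 − q) × 0.01]. The new count is 450 × (1 − q) × 0.01.

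| q (assumed) | Status count | New count |
|---|---|---|
| 0% | 4.5 | 4.5 |
| 1% | 9.0 | 4.5 |
| 2% | 13.4 | 4.4 |
| 5% | 26.8 | 4.3 |

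**4. What happens to the comparison of arms?** Assume new-onset rates of 0.5% and 1.5%. The counted rate is b + (1 − b)d, where b is the background and d the new-onset rate. The counted difference is (1 − b) × 1.0 point. The standard error is √[(p1(1 − p1) + p2(1 − p2))/450].

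| b (assumed) | Counted difference (points) | SE (points) |
|---|---|---|
| 0% | 1.00 | 0.66 |
| 1% | 0.99 | 0.93 |
| 2% | 0.98 | 1.13 |
| 3% | 0.97 | 1.30 |

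The difference hardly moves; the noise around it grows. With equal new-onset rates the expected difference stays zero.

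**5. Which ECG is the baseline?** Protocol Table 1 schedules ECGs at Visits 1, 3, 4, 5 and 6. The Visit 2 list in 6.2 contains none, and 6.3 places the Visit 3 ECG after the colonoscopy, hence after dosing. The only scheduled pre-dose ECG is at Visit 1. Against this, 7.2.4 says an ECG is taken at every visit and puts Randomization Visit in brackets after the baseline ECG. Exclusion criterion 12 also speaks of ECG findings at Visit 1 or Visit 2.

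**6. The AE sentence beside its neighbours.** Protocol 7.2.1 limits AEs from physical examination to new or worsened findings. The last sentence of 7.2.4 has no such limit. The note in Protocol 8.1 says that "pre-existing conditions diagnosed through assessments and examinations at the Screening Visit" are not AEs but medical history, which supplies the limit if the site reads the two sections together.

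**The case against.** A reader might infer that pre-existing ECG abnormalities end up counted as effects of the preparation. The documents do not support that. Protocol 7.2.4 sends the remaining baseline findings to medical history, and the 8.1 note excludes conditions found at screening. The definition in Protocol 9.8.2 and SAP 10.2 requires onset after the start of study drug or worsening of a prior condition. Causality is rated separately for each event (Protocol 8.2.2). The rule in 8.2.2 that dates an examination finding to the examination day applies once something is an AE; it does not make a medical-history item into one. What stands is an ambiguity in 7.2.4 that a site could read literally.

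A reader might also infer that the SAP reports no ECG change at all, or that carry-over hides a difference between formulations. The first is wrong because PR, QRS and QTc changes are summarised. The second fails on step 4: the absolute difference is almost unchanged, and the SAP plans no ECG ratio, interval or test (SAP 10.1).

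Three further points are fair. Exclusion criteria 8 and 12 screen out many relevant cardiac findings, so the background may be close to zero. The status table covers every assessment time, so screening status should be visible by arm, and the listings would allow a hand count. The two-visit wording has little practical effect, because only Visit 1 has a scheduled pre-dose ECG. None of these supplies the incidence table that Protocol 9.8.4.2 promises. SAP Section 14 puts the table shells in a separate document, which was not available; a shift table may exist there, but the SAP text does not call for one.

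**Conclusion.** The concern holds as a gap between endpoint and output. The SAP text does not produce the incidence of clinically significant ECG changes, does not declare the omission, and does not define the ECG baseline on which its change statistics rest. The 7.2.4 wording is a secondary consistency point.

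The consequence is confined to descriptive safety reporting; the primary endpoint and the efficacy tests are untouched. The status table overstates new abnormalities by about the number of subjects who carry an abnormal-CS rating from screening: roughly 9 per arm at an assumed 2%, none at 0%. Because treatment is randomised, this carry-over is expected equally in both arms. It raises the level and adds noise without biasing the comparison. The prevalence figures are assumptions, as the documents give none, and the calculation supposes that baseline ratings persist.

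**What to change.** **SAP 10.4.2.** Define the ECG baseline as the last ECG before the first dose of study drug, matching 10.3 and 10.4.1. Add a shift table by arm and visit from baseline rating to post-baseline rating, with the count of subjects newly rated abnormal-CS. Show subjects abnormal-CS at baseline as their own row and do not drop them. The three-level rating cannot show further deterioration in that row, so worsening there is captured through AEs. Keep the status table as support. If the sponsor decides against the shift table, Section 12 should declare the omission, though the endpoint would then remain unreported.

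**Protocol 7.2.4.** In the last sentence, limit AEs to clinically relevant abnormalities that are new or worsened against the baseline ECG, in line with 7.2.1 and 8.1. Reconcile the baseline visit and the statement on ECG frequency with Table 1 and 6.2, and check exclusion criterion 12 for the same Visit 2 reference.

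**Cost.** One sentence and one table in the SAP, from ratings already collected, in a format the SAP already uses for laboratory shifts (10.3.2), plus small wording changes in the protocol. No new assessments are needed.
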